## **5.5 Early Termination of Study**

The study may be terminated at any time by the Sponsor for reasons including but not limited to the following (i) if serious side effects occur, (ii) if the Investigator does not adhere to the protocol, (iii) if, in the Sponsor's judgment, there are no further benefits to be achieved from the study, or (iv) for administrative reasons. In the event that the clinical development of the investigational product is discontinued, Ardelyx, Inc. shall inform all Investigators / institutions and IRBs overseeing the trial.

## **5.6 Restrictions to Patients**

- For males and fertile females: Adherence to the precautions aiming at avoiding a pregnancy, including males not donating sperm, and therefore use of contraceptive methods as outlined in the Inclusion criteria ([Section 5.1](#)).

## 6 TREATMENT OF PATIENTS

### 6.1 Administration of Investigational Product

#### 6.1.1 Identity of Investigational Product(s)

##### 6.1.1.1 Study drug

Tenapanor hydrochloride is an amorphous, off-white to white powder. [REDACTED]

A matching placebo will be identically supplied in HDPE bottles.

##### 6.1.1.2 Active control

Sevelamer carbonate will be supplied, as commercially available. Each bottle contains two-hundred seventy (270) 800 mg tablets.

#### 6.1.2 Treatments Administered

Tablets containing 10 mg of tenapanor or corresponding placebo will be taken twice daily PO just prior to breakfast and dinner. On dialysis days, patients on HD should **not** take study drug at the meal prior to dialysis and instead take it before another meal. Each dose of one to three tablets will achieve total daily doses of 20, 40, or 60 mg tenapanor. If a meal is skipped, the dose should be taken with another meal during the day or at around the time that the meal would have been consumed.

During the randomized withdrawal period, patients in the tenapanor group will be randomized to either remain on their current dose of tenapanor or switched to placebo in a 1:1 ratio.

During the safety extension period, patients will continue with the same dose from the end of the 26-week treatment period. Titration is allowed as described for the 26-week treatment period.

Patients in the active control group will receive sevelamer carbonate for the entire 52 week study period.

##### 6.1.3 Dose Adjustments

All patients in the tenapanor group will start at a dose of 30 mg bid. After randomization (Visit 5) to Day 183 (Visit 13), doses can be adjusted in 10 mg increments based on serum phosphorus levels and/or GI tolerability. Down-titration can go from 30 mg bid to 20 mg bid and 20 mg bid to 10 mg bid. Dose escalation can go from 10 mg bid to 20 mg bid, and 20 mg bid to 30 mg bid.

##### 6.1.3.1 Discontinuation criteria

See [Section 5.4 Patient Withdrawal](#)

#### 6.1.4 Method of Assigning Patients to Treatment Groups

The CRO or designated statistician will prepare the randomization scheme in accordance with its standard operating procedures (SOPs) and the randomization plan, which reflect Good Clinical Practice (GCP) standards.

After obtaining informed consent, patients will be allocated sequential enrollment numbers in their order of completing Screening assessments.

Patients will be randomized after the washout period 3:1 to receive tenapanor or the active control, sevelamer carbonate. Patients in the tenapanor group will be randomized a second time at the end of the 26-week treatment period to enter into the randomized withdrawal period (Visit 13) to either remain on their current dose of tenapanor or a matched placebo in a 1:1 ratio. Randomization codes will be assigned via an Interactive Response Technology (IRT).

The IRT will allocate the treatment and provide the randomization number for both the 26-week treatment period and the randomized withdrawal period. The IRT will provide the appropriate bottle ID chosen from those bottle IDs available at the study site for tenapanor and placebo only. The randomization is carried out at study level and the assigned randomization numbers and the associated bottle IDs will not be sequential within a study site. The active control will not have unique bottle ID #s.

If a patient withdraws from participation in the study, then his/her enrollment/ randomization code cannot be reused.

### 6.2 Investigational Product Storage and Accountability

#### 6.2.1 Storage Conditions

The Investigator will ensure that all the study drug and active control are stored and dispensed in accordance with Food and Drug Administration (FDA) regulations concerning the storage and administration of investigational drugs.

Tablets of tenapanor and placebo should be stored in the original packaging according to the labeling. The active control should also be stored in the original packaging according to the labeling.

[figure not shown]
#### 6.2.2 Drug Accountability

The Investigator must ensure that all drug supplies are kept in a secure locked area with access limited to those authorized by the Investigator. The Investigator or the Investigator's designee must maintain accurate records of the receipt of all study drug and active control shipped by the Sponsor or its representative, including but not limited to the date received, lot number, amount received, and the disposition of all study drug. Current dispensing records will also be maintained including the date and amount of study drug and active control dispensed and the

patient receiving the drug. All remaining study drug not required by regulations to be held by the clinical facility must be returned to Sponsor or its representative immediately after the study is completed using the study drug return form provided.

### **6.3 Packaging and Labeling**

#### **6.3.1 Study Drug**

 Tablets of study drug should be stored in the original packaging according to the labeling.

#### **6.3.2 Blinding Methods**

The 26-week treatment period and the safety extension period are open labeled periods and study drug will not be blinded.

In the randomized withdrawal period, the treatment will be administered in a double-blind fashion. The active and placebo tablets are identical in appearance (shape, color, size, etc.).

Only the party responsible for labeling, warehousing and shipping drug supply, the study statistician, responsible for preparing the randomization list, and the IRT manager responsible ensuring drug is available at sites will have knowledge of the treatments assigned during the randomized withdrawal period.

The active control, sevelamer carbonate, will be administered as commercially packaged and used for the entire 52-week study period for patients randomized into that group.

### **6.4 Procedure for Breaking Randomization Code**

#### **6.4.1 Emergency Unblinding**

During the course of the randomized withdrawal period, the blind is to be broken only when the safety of the patient is at risk and knowledge of the treatment is essential to the clinical management of the patient. A decision to unblind a patient must be made in concert with the Medical Monitor and the Sponsor, except in an emergency situation when the blind must be broken to determine treatment for the patient. If a patient is unblinded, the date and reason for the unblinding must be recorded on the source documents. Please refer to [Section 7.3.6](#) for reporting requirements.

### **6.5 Prior and Concomitant Therapy**

#### **6.5.1 Prior Therapy**

This is a study in ESRD-HD and ESRD-PD patients with hyperphosphatemia. Patients with prior therapy specified in the exclusion criteria ([Section 5.2](#)) will not be eligible for entry into the study.

## 6.5.2 Concomitant Therapy

The use of concomitant medications during the study, unless needed to treat an AE, should be the same as the medications used and recorded at screening and during the washout period.

All previous medication (prescription and over-the-counter), vitamin and mineral supplements, and herbs taken by the participant in the past 30 days will be recorded in the medical history section of the patient's eCRF and will include start and stop date, dose and route of administration, frequency, and indication. Medications taken for a procedure should also be included.

### 6.5.2.1 Prohibited Medications

The use of phosphate binders other than sevelamer carbonate used in the active control group are prohibited. Phosphate binders include but are not limited to the following:

- Sevelamer carbonate and hydrochloride (Renvela®, Renagel®)
- Lanthanum carbonate (Fosrenol®)
- Sucroferric oxyhydroxide (Velphoro®)
- Ferric citrate (Auryxia®)
- Calcium carbonate (Tums®)
- Calcium acetate (PhosLo®)

## 7 COLLECTION OF STUDY VARIABLES

### 7.1 Recording of Data

The Investigator will ensure that data are recorded in the electronic Case Report Form (eCRF) for this study. The Investigator ensures accuracy, completeness, and timeliness of the data recorded and of the provision of answers to data queries. The Investigator will sign the completed eCRF and a copy of the completed eCRF will be archived.

### 7.2 Data Collection Prior to Enrollment

During Screening and the Wash-out Period, e.g., after signing the informed consent but prior to enrollment, the following information will be collected from every potential patient for baseline demographics as well as to assess each patient's suitability to participate in this study protocol:

- Assessment of the disease status outlined in the inclusion/exclusion criteria
- Date of birth, gender, and race
- Weight (pre-dialysis) and height (kg and cm, respectively)
- Kt/V – most recent value prior to screening
- KDQoL survey
- DSI survey (for English speakers only)
- Medical and surgical history
- Phosphate binder currently used and dose
- Physical examination
- Vital signs (pre-dialysis)
- Electrocardiogram (ECG) evaluation
- Blood sample for clinical laboratory chemistry and hematology tests, and virology laboratory tests (pre-dialysis)
- FSH and pregnancy test, if applicable
- Blood sample for Ca x P product, FGF23 and exploratory biomarkers
- Concomitant medications

### 7.3 Safety Variables

Safety assessments will be performed during the study and will include physical examinations, vital signs, body weights, clinical laboratory tests, electrocardiograms, and adverse event recording. Body weight, vital signs and blood collections for laboratory assessments **must** be performed predialysis. All other assessments may be performed pre-, during, or post-dialysis but should be performed at the same time at each visit. See [Section 8](#) (Methodology/Study Visits) for a detailed schedule of procedures.

### 7.3.1 Physical Examination

The physical examination will include an assessment of the following items: general appearance, skin (including any pitting edema in lower legs / feet), cardiovascular, respiratory, abdomen. Any findings or absence of findings relative to each patient's physical examination will be carefully documented in the patient's eCRF.

### 7.3.2 Vital Signs (blood pressure and heart rate)

Blood pressure and heart rate will be obtained at all patient visits (pre-dialysis). Blood pressure, sitting systolic and diastolic blood pressure (SSBP and SDBP) will be measured after the patient has been sitting for approximately 5 minutes. All measurements will be recorded on the source document and in the eCRF.

### 7.3.3 Electrocardiograms

A 12-lead electrocardiogram (ECG) will be performed in the sitting or supine position (for at least 5 minutes). The ECG must be transmitted to the central ECG site (Medpace Core Lab).

The following ECG parameters will be recorded: heart rate, PR-interval, QRS (principal deflection in ECG)-duration, QT-interval (uncorrected), QTc-interval (corrected), RR-interval.

The Investigator will assess any abnormalities upon receiving an email alert from Medpace Core Lab; abnormalities will be classified as clinically significant and not clinically significant. Electrocardiographic intervals and Investigator assessment of all abnormal ECGs will be recorded on the eCRF.

Additional ECGs may be obtained if clinically indicated.

### 7.3.4 Clinical Laboratory Tests

Samples **must** be obtained, pre-dialysis, for the clinical laboratory tests identified in [Table 7-1](#). A coagulation profile will only be performed on patients taking warfarin.

Other evaluations and tests performed during Screening and other time points, specified in the Schedule of Events ([Section 1.3](#)) will include:

- Serology screen, i.e., HBsAg, HCV, and HIV
- FSH test will be performed on all females at Screening
- Pregnancy test, if applicable

### 7.3.5 Analysis of Clinical Laboratory Tests

A certified laboratory will be used to process and provide results for the clinical laboratory tests. The baseline laboratory test results for clinical assessment for a particular test will be defined as the last measurement prior to the initial dose of study drug or active control.

For any laboratory test value outside the reference range that the Investigator considers clinically significant, the Investigator will:

- Repeat the test to verify the out-of-range value.
- Follow the out-of-range value to a satisfactory clinical resolution.
- Record as an AE any laboratory test value that (1) is confirmed and the Investigator considers clinically significant, or (2) that requires a patient to be discontinued from the study, or (3) that requires a patient to receive treatment, or (4) fulfills one or more SAE criteria.

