#### **3.2 Secondary Objectives**

The secondary objectives of this study are:

- To compare the phosphorus lowering effect between tenapanor and placebo based on the change in serum phosphorus (s-P) from the end of the 26-week treatment period to the end of the randomized withdrawal period or the endpoint visit for this period in the intent-to-treat (ITT) analysis set and at individual doses of tenapanor and placebo in both the efficacy and ITT analysis sets.
- To evaluate the effect of tenapanor on the change in serum phosphorus levels from baseline to the end of 26-week treatment period
- To evaluate the effect of tenapanor on the number of patients reaching serum phosphorus goal levels defined as < 5.5 mg/dl during the 26-week treatment period.
- To evaluate the effect of tenapanor on Calcium- Phosphorus Product (Ca x P) during all three study periods (26-week treatment period, randomized withdrawal period and safety extension period).
- To evaluate the effect of tenapanor on intact fibroblast growth factor 23 (iFGF23) and c-terminal FGF23 (cFGF23) levels during all three study periods (26-week treatment period, randomized withdrawal period and safety extension period).
- To evaluate the effect of tenapanor on the Kidney Disease Quality of Life (KDQoL) survey during all three study periods.
- To evaluate the effect of tenapanor on the Dialysis Symptom Index (DSI) survey during all three study periods (for English speakers only).
- To compare the long-term safety of tenapanor to the active control sevelamer carbonate.

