### 5.4 Patient Withdrawal

Patients are free to discontinue the study at any time, for any reason, and without prejudice to further treatment. The Investigator may remove a patient if, in the Investigator's judgment, continued participation would pose unacceptable risk to the patient or to the integrity of the study data. Some study specific discontinuation criteria will also apply to study participants receiving tenapanor or placebo:

- **Hypophosphatemia:** Serum phosphorus  $\leq 2.5$  mg/dL at any time.
- **Hyperphosphatemia:**
  - Serum phosphorus  $\geq 10.0$  mg/dL any time after Week 2 of the 26-week treatment period
  - Serum phosphorus  $\geq 9$  mg/dL for two consecutive visits after Week 2 during the 26-week treatment or safety extension period
  - Serum phosphorus  $\geq 9$  mg/dL during the randomized withdrawal period

Patients discontinued from the randomized withdrawal period will be offered the opportunity to enter the open-label safety assessment period or be discontinued from the study and return to standard of care.

Patients in the active control group, receiving sevelamer carbonate do not have specific discontinuation criteria; they will be treated based on standard of care using the package insert for guidance.

A patient who discontinues will always be asked about the reason(s) for discontinuation and the presence of any AEs. The Investigator will record the reason for early withdrawal in the eCRF.

If a patient discontinues the study, all visit procedures for Visit 23 will be completed, if possible.

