**Table 7-1 Clinical Laboratory Tests**

Hematology a	Chemistry b	Coagulation Profile c,d	Serology c	Other e
Hematocrit Hemoglobin Red blood cell (RBC) count White blood cell (WBC) count Neutrophils (%) Lymphocytes (%) Monocytes (%) Basophils (%) Eosinophils (%) Platelet count	Albumin Alanine aminotransaminase (ALT) Aspartate aminotransaminase (AST) Alkaline phosphatase Bilirubin, total Bicarbonate Blood urea nitrogen (BUN) Calcium, total Chloride Creatinine Creatine kinase Glucose Magnesium Phosphorus f Potassium Ca x P j Sodium	Prothrombin time Activated partial thromboplastin time	Hepatitis B infection Hepatitis C infection Human immunodeficiency virus	FSH g Serum pregnancy g FGF-23 h,j Parathyroid Hormone (PTH) c

a Whole blood.

b Serum.

c Plasma.

d Only in people treated with Warfarin.

e Not part of standard clinical laboratory tests, must be specified; performed at specified time points.

f Serum phosphorus is also performed separately from standard clinical laboratory tests at protocol specified time points.

g FSH and serum pregnancy tests are performed on all females at Screening. After screening, pregnancy tests will only be performed on females of child-bearing potential unless FSH at screening indicates post-menopausal status.

h Both intact and c-terminus FGF-23 will be measured.

j Used in efficacy analyses

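### AE recording of extreme serum phosphorus is partly rule-driven on tenapanor but left to investigator judgment on open-label sevelamer, which can distort the safety comparison between them

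*Combined protocol and SAP*

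**What the plan says.** Section 7.3.5 opens with a condition that applies to every arm: "For any laboratory test value outside the reference range that the Investigator considers clinically significant, the Investigator will" repeat the test, follow the value to resolution, and record AEs by a list of routes. The recording instruction begins "Record as an AE any laboratory test value that (1) is confirmed and the Investigator considers clinically significant" and continues "or (2) that requires a patient to be discontinued from the study, or (3) that requires a patient to receive treatment". A fourth route covers values that meet a criterion for a serious AE.

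Phosphorus is listed under chemistry in Table 7-1, with a footnote that "Serum phosphorus is also performed separately from standard clinical laboratory tests at protocol specified time points". Nothing exempts s-P from Section 7.3.5.

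Section 5.4 introduces its numeric s-P limits with "Some study specific discontinuation criteria will also apply to study participants receiving tenapanor or placebo". For the other arm it says: "Patients in the active control group, receiving sevelamer carbonate do not have specific discontinuation criteria". Those patients are managed by standard of care.

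Section 4.1 says that the sevelamer group is there for safety analysis, and Section 3.2 lists as a secondary objective "To compare the long-term safety of tenapanor to the active control sevelamer carbonate". Under Section 6.3.2 the 26-week and extension periods are open label. Section 9.4.8 tabulates treatment-emergent AEs by treatment group, separately for each study period.

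**The concern.** A fair comparison of AE rates needs the same event to have the same chance of being recorded in each arm. Here the recording list refers to a consequence, discontinuation, that the protocol attaches to fixed s-P values in one arm only. A site that follows both sections has a written reason to log a threshold s-P as an AE on tenapanor. For the same value on sevelamer it has only its own judgment, exercised with treatment known.

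At stake is the comparison that the sevelamer arm was included to provide. Part of any difference in phosphorus AEs could reflect the recording rule rather than the drugs. The same holds for AEs leading to discontinuation, which can be derived because Section 7.3.6.2 records drug withdrawal as an action taken.

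**Working it through.** The plan gives no figure on this point: no expected rate of s-P stops and no rate of AE recording. The check is therefore a side-by-side reading, followed by an illustration on stated assumptions.

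**1. Routes to an AE, by arm (26-week and extension periods)**

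| Route in 7.3.5 | Tenapanor | Sevelamer |
|---|---|---|
| (1) confirmed and clinically significant | investigator judgment | investigator judgment |
| (2) forces discontinuation from the study | reached by a fixed s-P value under 5.4 | no fixed value; only if the investigator removes the patient on general grounds |
| (3) needs treatment | open | open; not stated whether a dose adjustment counts |
| (4) serious AE criterion | open | open |

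Only route (2) differs by rule.

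**2. Where the difference matters most.** Route (1) asks for confirmation and route (2) does not. Of the Section 5.4 limits that apply outside the withdrawal period, ≥9 mg/dL needs two consecutive visits and so carries its own repeat. The limits ≤2.5 mg/dL and ≥10 mg/dL act on a single value. One unconfirmed value of that kind can be an AE on tenapanor under route (2). On sevelamer it needs confirmation, treatment, a serious criterion or a discretionary withdrawal.

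Section 4.1 applies the ≥10 limit in the extension as well, whereas the Section 5.4 bullet names only the 26-week period. The two need reconciling, because this decides which extension values can reach route (2).

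**3. Opportunity to observe.** The schedules match in the 26-week period and from Visit 19 to Visit 23. After Visit 13 and up to Visit 19, tenapanor-group patients have six s-P visits (14 to 19). Sevelamer patients have three (15, 17 and 19), because Visits 14, 16 and 18 are omitted for them. Raw counts of threshold values over 52 weeks are therefore not comparable unless restricted to common visits.

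**4. Illustration of size.** Arm sizes follow Section 9.2: 560 x 3/4 = 420 tenapanor and 560 x 1/4 = 140 sevelamer. Assume the same true share p of patients with a threshold s-P in each arm, all of them recorded as AEs on tenapanor, and a share q of them recorded on sevelamer.

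Spurious difference = p - pq = p(1-q)

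| p | q | Tenapanor AEs (420 x p) | Sevelamer AEs (140 x p x q) | Difference (points) |
|---|---|---|---|---|
| 2% | 0 | 8.4 | 0 | 2 |
| 2% | 0.5 | 8.4 | 1.4 | 1 |
| 2% | 1 | 8.4 | 2.8 | 0 |
| 5% | 0 | 21 | 0 | 5 |
| 5% | 0.5 | 21 | 3.5 | 2.5 |
| 5% | 1 | 21 | 7 | 0 |
| 10% | 0 | 42 | 0 | 10 |
| 10% | 0.5 | 42 | 7 | 5 |
| 10% | 1 | 42 | 14 | 0 |

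Both p and q are assumptions. If only a share r is recorded on tenapanor, because the investigator also applies the opening condition there, the difference becomes p(r-q). It vanishes when r = q.

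**The case against.** The strongest reply is that Section 7.3.5 is not arm-specific. Its opening condition limits the whole list to values that the investigator considers clinically significant, so route (2) does not stand alone. Its first instruction is to repeat such values in any arm, which often leads to route (1). Routes (1), (3) and (4) are open on sevelamer. This stands, and it rules out a reading that a reader might infer: that a given s-P is an AE on tenapanor and is not one on sevelamer. That is the q = 0 row of the illustration, which the documents do not establish. What remains is that a value obliging the site to stop a patient is hard to call insignificant, so the protocol steers the judgment in one arm only.

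A reader might also infer that in the randomized withdrawal period the rule turns loss of phosphate control into AEs and makes placebo look less safe. The text does not support this. Route (2) refers to discontinuation from the study, and Section 5.4 offers patients stopped in that period entry to the extension. The limit is the same for tenapanor and placebo, under double-blind treatment. Sevelamer patients do not enter that period.

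Three further points limit the weight. The primary safety objective names no comparator; the sevelamer comparison is secondary. Section 9.4.8 plans descriptive summaries by preferred term, so phosphorus events could be separated afterwards, and it describes no table of AEs leading to discontinuation. Finally, any excess would fall on the investigational arm, which is the cautious direction for tenapanor. That is reassuring about the direction, but it does not make the comparison accurate.

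**Conclusion.** The point holds as a difference in ascertainment. Recording of extreme s-P as an AE is partly driven by rule on tenapanor and left to open-label judgment on sevelamer. This affects a stated secondary objective in the 26-week and extension periods. It rests on three facts in the protocol: s-P is a Section 7.3.5 test without exemption, route (2) needs no confirmation, and numeric s-P limits exist only for tenapanor and placebo.

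The size cannot be determined from the documents. Under the assumptions above it is p(1-q), from zero when sevelamer sites record every threshold value up to p when they record none. The protocol does not show that the second case would occur. This is a cheap improvement to make before the data are summarized, and not a flaw that invalidates the safety analysis.

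**What to change.** 1. In Section 7.3.5, state one rule for whether an s-P value that reaches a Section 5.4 threshold is recorded as an AE. Apply it identically in all arms, whether or not the value forces discontinuation. State also whether a change in phosphate-lowering treatment counts under route (3).
2. Record s-P stops as their own disposition reason.
3. Tabulate s-P ≤2.5, ≥9 and ≥10 mg/dL by arm from central laboratory data, at visits common to both arms (so without Visits 14, 16 and 18).
4. Show AEs leading to discontinuation with and without events that arose only from an s-P criterion.

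Simply taking stop-triggering s-P out of the tenapanor AE tables would be debatable, because unconfirmed values, including low ones, could vanish from the investigational arm's AE record. A common rule avoids that.

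The cost is a short addition to Section 7.3.5, one eCRF category and one or two extra tables. No stopping rule changes.
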